## **US (FDA)**

With 750 randomized subjects (Intention To Treat Set [ITT]), the study will provide at least 99% power to demonstrate statistical non-inferiority of roxadustat versus ESA in the primary endpoint for US submission.

### **7.2 Analysis Set**

Detailed criteria for analysis sets will be laid out in Classification Specifications and the allocation of subjects to analysis sets will be determined prior to database hard-lock.

The following analysis sets are defined and will be used for the statistical analysis:

- Intention To Treat Set (ITT)
- Full Analysis Set (FAS)
- PPS
- Safety Analysis Set (SAF)
- Pharmacokinetic Analysis Set (PKAS)

#### **7.2.1 ITT**

All randomized subjects will be included in the ITT.

The primary US endpoint will be analyzed using the ITT. The primary EU endpoint and selected secondary efficacy endpoints will be analyzed using the ITT in secondary analyses.

#### **7.2.2 FAS**

All randomized subjects who received at least 1 dose of study drug and have at least 1 postdose Hb assessment will be included in the FAS.

The primary US and EU endpoints will be analyzed using the FAS in secondary analyses. Selected secondary efficacy endpoints will be analyzed using the FAS.

#### **7.2.3 PPS**

All FAS subjects who received at least 12 weeks of study treatment with at least 1 postdose Hb assessment and without any criteria for PPS exclusion will be included in the PPS.

Criteria for PPS exclusion will be defined in the SAP. The primary EU endpoint will be analyzed using the PPS. Selected secondary efficacy endpoints will be analyzed using the PPS.

Additional PPS sub-populations (e.g. PPS-36) will be described in the SAP.

#### **7.2.4 SAF**

All subjects that received at least 1 dose of study drug will be included in the SAF. All safety data will be analyzed using the SAF.

#### **7.2.5 PKAS**

The PKAS consists of all randomized subjects who meet the following criteria:

- Received at least 1 dose of study drug, and

- At least 1 quantifiable plasma concentration of roxadustat was obtained and dosing and sampling history has been recorded.

The PKAS will be used for all tables and graphical summaries of the population PK analysis.

### **7.3 Demographics and Other Baseline Characteristics**

Demographic (age, race, sex) and other baseline characteristics, including stratification factors, and subject disease characteristics will be summarized for the SAF, FAS, ITT and PPS populations.

Descriptive statistics will be calculated for continuous variables (e.g., age, weight, baseline Hb, body mass index, and average weekly ESA [epoetin and darbepoetin alfa] dose in last 4 weeks prior to randomization) by treatment arm. Frequency counts and percentages will be tabulated for categorical variables (e.g., sex, race, previous ESA treatment, average prescribed weekly ESA [epoetin and darbepoetin alfa] dose in last 4 weeks prior to randomization [categorical], baseline Hb [categorical], region, mode of dialysis, and history of cardiovascular, cerebrovascular or thromboembolic disease) by treatment arm.

### **7.4 Analysis of Efficacy**

#### **7.4.1 Analysis of Primary Endpoint**

There are 2 separate regionally based primary efficacy endpoints in this study, depending upon whether the data are being filed to support submission to the US FDA or to Ex-US health authorities, such as the EMA.

- The EU (EMA) primary efficacy endpoint is change in Hb from BL to the average level during the evaluation period (defined as week 28 until week 36), without having received rescue therapy (i.e. RBC transfusion for all subjects or ESA for subjects treated with roxadustat) within 6 weeks prior to and during this 8-week evaluation period.
- The US (FDA) primary efficacy endpoint is change in Hb from BL to the average level during the evaluation period (defined as week 28 until week 52), regardless of rescue therapy.

The central laboratory reported Hb values will be used for this analysis.

#### **7.4.1.1 Primary Analysis**

##### **EU (EMA)**

The EU primary efficacy endpoint will be analyzed using a Mixed Model Of Repeated Measures (MMRM) method with an unstructured covariance matrix. The model will contain terms for treatment arm, baseline Hb measurement, visit, visit x treatment arm and other stratification factors.

For subjects who require rescue therapy, the reported values after the initiation of rescue therapy will be set to missing for 6 weeks; the MMRM model will implicitly impute missing data via the within-patient correlation structure.

Difference of least square means (roxadustat minus ESA) and its  $100 \times (1 - \alpha^2)\%$  CI will be estimated for the average of weeks 28 to 36. The significance level  $\alpha$  is fixed by the parametric chain procedure explained below.

The primary analysis of the EU primary efficacy endpoint will be tested both in the overall population and in the subgroup of patients defined as subjects with an average prescribed weekly epoetin or darbepoetin dose within the last 4 weeks prior to randomization  $\leq 200$  IU/kg or  $\leq 1$   $\mu\text{g}/\text{kg}$ , respectively, following a parametric chain procedure [Millen et al., 2011; Spiessens et al, 2010].

The 2 null hypotheses to be tested are:

- $H_{A0}$ : Hb change from baseline in the roxadustat arm  $\leq$  Hb change from baseline in the ESA arm minus 0.75 g/dL in the total study population
- $H_{B0}$ : Hb change from baseline in the roxadustat arm  $\leq$  Hb change from baseline in the ESA arm minus 0.75 g/dL in the subgroup population

The alternative hypotheses  $H_{A1}$  and  $H_{B1}$  are defined as the negation of the null hypotheses  $H_{A0}$  and  $H_{B0}$  respectively. The information fraction will be calculated at the time of database hardlock as the number of subjects in the subgroup with respect to the number of subjects in the total study population.

The overall 1-sided significance level (alpha) is fixed at 0.025. The overall alpha will be equally allocated to each of the 2 null hypotheses defined above. In case of an information fraction of 0.80, this rule will lead to significance level of 0.0174. Following the parametric chain procedure, if at least 1 of both hypotheses is rejected at the significance level of 0.0174, the other 1 can be tested at a significance level of 0.025 while still strongly controlling the overall type I error. The study will be successful for the EU primary efficacy endpoint if either of the null hypotheses is rejected, i.e. if the lower limit of the 2-sided  $100 \times (1 - \alpha^2)\%$  CI for the difference in least square means from the MMRM model is greater than -0.75g/dL.

The EU primary analysis will be tested on the PPS.

The analysis will be repeated on the FAS and ITT as secondary analyses. In addition, an Analysis of Covariance (ANCOVA) model with Last Observation Carried Forward (LOCF) will be used for imputation of missing values (see Section [7.4.1.2](#) for secondary analyses).

### **US (FDA)**

The US primary efficacy endpoint will be analyzed using an MMRM method with an unstructured covariance matrix. The model will contain terms for treatment arm, baseline Hb measurement, visit, visit x treatment arm and other stratification factors.

The null hypothesis to be tested for the US primary efficacy analysis is:

- $H_0$ : Hb change from baseline in the roxadustat arm  $\leq$  Hb change from baseline in the ESA arm minus 0.75 g/dL

The alternative hypothesis  $H_1$  is defined as the negation of the null hypothesis  $H_0$ . The overall 1-sided significance level (alpha) is fixed as 0.025. The study will be successful for the US primary endpoint if the null hypothesis is rejected.

The US primary analysis will be tested on the ITT.

The analysis will be repeated on the FAS and PPS as secondary analyses. In addition, an ANCOVA model with LOCF will be used for imputation of missing values (see Section 7.4.1.2 for secondary analyses).

#### Justification of the non-inferiority margin

The clinical importance of a -0.75 g/dL change in Hb has been selected whilst taking into consideration the biological variability in Hb, the effect on Hb from transfusing a single unit of packed RBCs, and clinical factors that affect Hb measurements.

#### **7.4.1.2 Secondary Analyses**

Interpretation of results will be based on the primary analysis sets (PPS for EU primary efficacy endpoint and ITT for US primary efficacy endpoint). Sensitivity (secondary) analyses with other analysis sets will be conducted to assess the robustness of the results from the statistical tests.

The same analysis of the primary endpoint as described in Section 7.4.1.1 will be repeated using the following analysis sets:

- For the EU primary efficacy endpoint, the FAS and the ITT,
- For the US primary efficacy endpoint, the PPS and the FAS.

Another sensitivity analysis for the EU and US primary efficacy endpoints will be performed to handle missing data using an ANCOVA model including baseline Hb and other stratification factors as covariates. Missing data will be imputed using the LOCF method.

In addition, a sensitivity analysis on the 2 primary efficacy endpoints (EU and US) will be performed on the subgroup of patients being randomized after the implementation of protocol v2.0, using the PPS (EU primary efficacy endpoint) and the ITT (US primary efficacy endpoint).

Additional sensitivity analyses will be described in the SAP.

#### **7.4.1.3 Subgroup Analysis**

The analyses will be repeated separately for the following subgroups:

- Subjects pretreated with epoetin versus subjects pretreated with darbepoetin alfa.
- HD (including hemodiafiltration) versus PD.
- Subjects with an average prescribed weekly epoetin or darbepoetin dose within the last 4 weeks prior to randomization  $\leq 200$  IU/kg or  $\leq 1$   $\mu$ g/kg versus subjects with an average  $> 200$  IU/kg or  $> 1$   $\mu$ g/kg respectively.

Other subgroup analyses will be described in the SAP.

## 7.4.2 Analysis of Key Secondary Endpoints

Once a primary hypothesis has been rejected for the EU primary efficacy endpoint, the secondary endpoints will be tested as described below using a fixed sequence testing procedure.

These tests will be performed only for the overall population in the case that the primary hypothesis was rejected for the overall study population. If the EU primary analysis was not successful for the overall population, but only for the subgroup, then the tests will be performed only for the subgroup. The subgroup population is defined as subjects with an average prescribed weekly epoetin or darbepoetin dose within the last 4 weeks prior to randomization  $\leq 200$  IU/kg or  $\leq 1$   $\mu$ g/kg.

The central laboratory reported Hb values will be used for this analysis.

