**Secondary Hypotheses**

Once a primary hypothesis has been rejected for the EU primary efficacy endpoint, the secondary endpoints will be tested as described below using a fixed sequence testing procedure. These tests will

be performed only for the overall population in the case that the primary hypothesis was rejected for the overall study population. If the EU primary analysis was not successful for the overall population, but only for the subgroup, then the tests will be performed only for the subgroup.

1. Proportion of Hb responders in the average of weeks 28 to 36 (noninferiority of roxadustat versus ESA) without having received rescue therapy. The non-inferiority margin for the difference between groups is 15%.
2. LDL cholesterol change from BL to the average of weeks 12 to 28 (superiority of roxadustat versus ESA)
3. Monthly IV iron (mg) use per subject during weeks 1 to 36 (superiority of roxadustat vs ESA).
4. SF-36 PF sub-score change from BL to the average of weeks 12 to 28 (noninferiority of roxadustat versus ESA). The noninferiority margin is fixed as a difference of 3 points.
5. SF-36 VT sub-score change from BL to the average of weeks 12 to 28 (noninferiority of roxadustat versus ESA). The noninferiority margin is fixed as a difference of 3 points.
6. MAP change from BL to the average MAP of weeks 20 to 28 (non-inferiority of roxadustat versus ESA). The noninferiority margin for the difference between groups is 1 mmHg.
7. Time to an increase in blood pressure during weeks 1 to 36 (non-inferiority of roxadustat versus ESA). The noninferiority margin is fixed as a hazard ratio of 1.3.
8. MAP change from BL to the average MAP of weeks 20 to 28 (superiority of roxadustat versus ESA).
9. Time to an increase in blood pressure during weeks 1 to 36 (superiority of roxadustat versus ESA).

The EU primary analysis will be tested on the PPS for the noninferiority tests and the FAS for the superiority tests.

The analysis will be repeated using (a) the FAS and ITT for noninferiority tests and (b) the PPS and ITT for superiority tests as secondary analyses

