### EU (EMA)

Results from simulations of the EU primary efficacy endpoint in stable dialysis subjects suggest that dosing levels of ESA prior to randomization may play a role in Hb response. Therefore, the EU primary analysis of this study will be tested both in the overall population and in the subgroup of patients defined as subjects with an average prescribed weekly epoetin or darbepoetin dose within the last 4 weeks prior to randomization  $\leq 200$  IU/kg or  $\leq 1$   $\mu\text{g}/\text{kg}$  respectively, following a parametric chain procedure [Millen et al, 2011; Spiessens et al, 2010]. The information fraction will be calculated at the time of database hard lock; it is defined as the number of subjects in the subgroup with respect to the number of subjects in the total study population.

Assuming that the Per Protocol Set (PPS) analysis will consist of 80% of the randomized subjects, 750 randomized subjects will lead to approximately 600 subjects in the PPS. The overall 1-sided significance level (alpha) is fixed at 0.025 and the non-inferiority margin for the EU primary endpoint has been fixed to 0.75 g/dL. The overall alpha will be equally allocated to each of the 2 test populations. If we assume an information fraction of 0.80, this rule will lead to a significance level of 0.0174.

In this setting, 300 subjects for the roxadustat treatment group and 300 subjects for the ESA treatment group will provide 97% power to statistically demonstrate noninferiority of roxadustat versus ESA in the EU primary endpoint in both the total study population and the planned subgroup analysis assuming a difference (roxadustat minus ESA) of -0.25 g/dL in the Hb change from baseline and an SD of 1.5 g/dL. In the case that these assumptions do not hold across the overall population, the planned procedure can still allow for a successful conclusion for the subgroup.

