4 SAMPLE SIZE

The study is sufficiently powered for both regionally-based primary efficacy endpoints. Approximately 750 subjects will be randomized to receive roxadustat or ESA in an open-label fashion in a 1:1 ratio.

EU (EMA)

Results from simulations of the EU primary efficacy endpoint in stable dialysis subjects suggest that dosing levels of ESA prior to randomization may play a role in Hb response. Therefore, the EU primary analysis of this study will be tested both in the overall population and in the subset (subgroup) of patients defined as subjects with an average prescribed weekly epoetin or darbepoetin dose within the last four weeks prior to randomization ≤ 200 IU/kg or ≤ 1 $\mu\text{g}/\text{kg}$ respectively, following a parametric chain procedure [Millen et al, 2011; Spiessens et al, 2010]. The information fraction will be calculated at the time of database hard lock; it is defined as the number of subjects in the subset with respect to the number of subjects in the total study population.

Assuming that the Per Protocol Set (PPS) analysis will consist of 80% of the randomized subjects, 750 randomized subjects will lead to approximately 600 subjects in the PPS. The overall one-sided significance level (alpha) is fixed at 0.025 and the non-inferiority margin for the EU primary endpoint has been fixed to -0.75 g/dL. The overall alpha will be equally

allocated to each of the two test populations. If we assume an information fraction of 0.80, this rule will lead to a significance level of 0.0174.

In this setting, three hundred (300) subjects for the roxadustat treatment group and 300 subjects for the ESA treatment group will provide 97% power to statistically demonstrate non-inferiority of roxadustat versus ESA in the EU primary endpoint in both the total study population and the planned subset population analysis assuming a difference (roxadustat minus ESA) of -0.25 g/dL in the Hb change from baseline and an SD of 1.5 g/dL. In the case that these assumptions do not hold across the overall population, the planned procedure can still allow for a successful conclusion for the subset population.

US (FDA)

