Table 12 Information Fraction (IF) and One Sided Significance Level (alpha) for the Primary Endpoint

Information Fraction (IF)	alpha (1-sided)
0.5	0.0147
0.6	0.0154
0.7	0.0162
0.8	0.0174
0.9	0.0191
0.97	0.0216

Following the parametric chain procedure, if at least one of the two null hypotheses is rejected at the significance level of 0.0174, the other one can be tested at a significance level of 0.025 while still controlling the overall type I error. The study will be successful for the EU primary efficacy endpoint if either of the null hypotheses is rejected, i.e., if the lower limit of the two-sided $100*(1-\alpha*2)\%$ CI for the difference in least square means from the MMRM model is greater than -0.75g/dL.

If both null hypotheses are rejected, secondary endpoints will be assessed on the overall population. Otherwise, secondary endpoints will not be formally tested.

The covariates will be:

- Previous ESA treatment (epoetin versus darbepoetin alfa);
- Region (region A versus region B);
- History of cardiovascular, cerebrovascular or thromboembolic diseases (Yes versus No)[#];
- Average prescribed weekly ESA dose prior to randomization (≤ 200 IU/kg epoetin or ≤ 1 μ g/kg darbepoetin alfa versus > 200 IU/kg epoetin or > 1 μ g/kg darbepoetin alfa)^{*};
- Baseline Hb value (Continuous).

[#]: This covariate is derived according to a list of cardiovascular disease preferred terms received from the study physician after softlock.

^{*}: For the analyses, the average prescribed weekly ESA dose prior to randomization will be taken from the screening procedure form, in the eCRF. Upon review of data, this covariate was excluded from analysis as number of subjects in the high dose group was too low for the variable to be meaningful.

For these covariates, the IRS value used at randomization will be compared to the eCRF value.

In case of stratification errors during the randomization process, the analysis will use the correct covariates as recorded on the eCRF for the subject.

MMRM model:

An MMRM model will be run for the purpose of implicit imputation of missing data by using all the available information from the observed data via the within-patient correlation

structure. The analysis will be based on the estimated difference between the two treatment arms overall mean effects throughout the evaluation period (weeks 28 to 36) based on this MMRM model.

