7.4.2 Analysis of Key Secondary Endpoints

Once the null hypothesis has been rejected for the EU (EMA) primary efficacy endpoint for both the total population and the subset population, the key secondary endpoints will be tested for the total population, as described below.

The EU (EMA) primary analysis set for the analysis of the key secondary endpoints will be the PPS for the non-inferiority tests and the FAS for the superiority tests.

All inferential analyses will evaluate the difference between the treatment arms: roxadustat versus ESA (i.e. pooled darbepoetin alfa and epoetin alfa).

The key secondary endpoints will be tested using a fixed sequence testing procedure, as depicted in [Table 17](#) in order to maintain the overall one-sided type I error rate for the set of key secondary endpoints at 0.025. If the null hypothesis is rejected for a test, the claim of superiority (or non-inferiority) will be considered successful and the test will progress to the next comparison in sequence as follows:

Table 17 Key Secondary Endpoints Fixed Sequence Testing Procedure

Test	Analysis sets	Endpoint	Comparison
1	PPS	Hb response defined as mean Hb during weeks 28 to 36 within the target range of 10.0 to 12.0 g/dL without having received rescue therapy within 6 weeks prior to and during this 8-week evaluation period.	Non-inferiority of roxadustat versus ESA (the non-inferiority margin for the difference between groups is -15%
2	FAS	Change from BL in Low Density Lipoprotein (LDL) cholesterol to the average LDL cholesterol of weeks 12 to 28.	Superiority of roxadustat versus ESA
3	FAS	Mean monthly IV iron use (mg) during day 1 to week 36 (monthly defined as a period of 4 weeks).	Superiority of roxadustat versus ESA
4	PPS	Change from BL in SF-36 Physical Functioning (PF) sub-score to the average PF sub-score of weeks 12 to 28.	Non-inferiority of roxadustat versus ESA (the non-inferiority margin is fixed as -3)
5	PPS	Change from BL in SF-36 Vitality (VT) sub-score to the average VT sub-score of weeks 12 to 28.	Non-inferiority of roxadustat versus ESA (the non-inferiority margin is fixed as -3)
6	PPS	Change from BL in mean arterial pressure (MAP) to the average MAP value of weeks 20 to 28.	Non-inferiority of roxadustat versus ESA (the non-inferiority margin for the difference between groups is 1 mmHg)

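### If exactly one EU primary null is rejected, the protocol opens formal testing of the key secondary endpoints and the SAP forbids it; neither document says which rule prevails

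*Protocol*

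**What the plan says.** The EU primary analysis tests two non-inferiority nulls: H_A0 in the overall population and H_B0 in the subgroup on lower prior ESA doses. A parametric chain links them. Each is tested first at a reduced one-sided level, 0.0174 at an information fraction (IF) of 0.80. If one is rejected, the other may be tested at 0.025. On success the documents agree. The SAP states "The study will be successful for the EU primary efficacy endpoint if either of the null hypotheses is rejected", and Protocol 7.4.1.1 has the same rule.

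They part at the gate to the key secondary endpoints.

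- **Protocol.** Section 7.4.2 begins "Once a primary hypothesis has been rejected for the EU primary efficacy endpoint, the secondary endpoints will be tested as described below". The sequence runs in the overall population if H_A0 is rejected. If the primary analysis was "not successful for the overall population, but only for the subgroup, then the tests will be performed only for the subgroup". The synopsis, under Secondary Hypotheses, gives the same branch: "If the EU primary analysis was not successful for the overall population, but only for the subgroup".
- **SAP.** Section 7.4.1.1.1 states "If both null hypotheses are rejected, secondary endpoints will be assessed on the overall population. Otherwise, secondary endpoints will not be formally tested". Section 7.4.2 repeats the condition: "Once the null hypothesis has been rejected for the EU (EMA) primary efficacy endpoint for both the total population and the subset population".

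Both documents keep the subgroup-only win as a design aim. Protocol 7.1 says "the planned procedure can still allow for a successful conclusion for the subgroup" and SAP section 4 says "the planned procedure can still allow for a successful conclusion for the subset population".

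**The concern.** The two gates give the same answer when both nulls are rejected and when neither is. They give opposite answers when exactly one is rejected, which both documents count as an EU success. In that branch the protocol starts a fixed sequence of up to nine confirmatory tests (it stops at the first failure), and the SAP starts none. A reader of a positive key secondary result could not establish from the documents whether it was confirmatory or descriptive. The trial is open-label, so a gate chosen once results are known would weaken any confirmatory label. The branch in dispute is also the one that the two-population strategy was built to exploit.

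**Working it through.** **The rules side by side**

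| Outcome | EU primary (both documents) | Protocol secondaries | SAP secondaries |
|---|---|---|---|
| Both nulls rejected | Success | Sequence, overall population | Sequence, total population |
| H_A0 only | Success | Sequence, overall population | No formal test |
| H_B0 only | Success | Sequence, subgroup | No formal test |
| Neither | Failure | None | None |

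**Is there a precedence rule?** Protocol section 7 and SAP section 1 require changes from the SAP to be justified in the study report. That covers departures from the SAP, not conflict between the SAP and the protocol. SAP section 1 describes the SAP as elaborating the protocol and cites protocol version 2.2; the current protocol is version 3.0. The SAP revision history (section 8) records a reordering of the key secondaries but no change of gate. Protocol Amendment 2 does not mention the gate.

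**The plan's own figures.** Solving 2a - P(Z1 > c, Z2 > c) = 0.025, with a the one-sided level of c and correlation sqrt(IF), gives a = 0.01737 at IF 0.80. This matches the stated 0.0174. The same formula reproduces every row of SAP Table 12 except IF 0.97, where it gives about 0.0214 to 0.0215 against 0.0216; this makes no material difference here. With 300 per arm, SD 1.5 and a distance to the margin of 0.75 - 0.25 = 0.50 g/dL, power is 97.6% for the overall population at 0.0174, 97.9% for at least one null and 95.1% for both. The stated figure is 97%.

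**How often is exactly one null rejected?** Inputs from Protocol 7.1 and SAP Table 12: 300 per arm, SD 1.5, margin -0.75 g/dL, subgroup difference -0.25 g/dL, first-step levels 0.0174, 0.0191 and 0.0216 at IF 0.80, 0.90 and 0.97, second-step level 0.025. The high-dose difference is not given, so it is varied as an assumption.

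- Overall SE = 1.5 x sqrt(2/300) = 0.1225; subgroup SE = 0.1225/sqrt(IF).
- Overall difference = IF x subgroup + (1 - IF) x high-dose.
- Overall statistic = sqrt(IF) x subgroup statistic + sqrt(1 - IF) x high-dose statistic.
- Exactly one = P(A > c, B < 1.96) + P(B > c, A < 1.96), with A the overall statistic, B the subgroup statistic and c the first-step critical value.

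For equal effects at IF 0.80, the means are 0.50/0.1225 = 4.08 (A) and 0.50/0.1369 = 3.65 (B). Overall-only is 2.65% and subgroup-only is 0.16%, together 2.81%.

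| IF | High-dose subjects in a PPS of 600 | High-dose -0.25 (as planned) | -0.75 | -1.25 | -1.75 |
|---|---|---|---|---|---|
| 0.80 | 120 | 2.8% | 5.1% | 25.1% | 56.7% |
| 0.90 | 60 | 1.2% | 1.7% | 6.1% | 14.9% |
| 0.97 | 18 | 0.45% | 0.5% | 0.9% | 1.7% |

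In the last three columns at IF 0.80, over 90% of the cases are subgroup-only (for example 4.68 of 5.08 points).

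**Pooled error, as context for choosing a gate.** Neither document promises control over primary and secondary tests together: Protocol 7.4.1.1 covers the two primary nulls and 7.4.2.1 the secondary set. Take the subgroup at the margin, the high-dose difference at 0 and a true secondary null tested at 0.025. Under the protocol gate, pooled error at IF 0.80 is 2.9% if the secondary is independent of the primary and 3.7% at an assumed correlation of 0.5. At IF 0.97 it is 2.4% to 2.5%. Under the SAP gate it is at most 2.5%. This is one scenario, not a bound. If one primary null is always rejected while the other primary null and the first secondary null are true and independent, the protocol gate gives 1 - 0.975 x 0.975 = 4.94%.

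**The case against.** The best counter-argument is that the SAP governs in practice. It is later (10 September 2018 against 30 May 2017), states its gate twice in consistent terms, and is the document against which changes are to be justified. Its gate is also the narrower, so anyone who follows it makes no claim that the protocol would disallow. The safe direction stands. Precedence does not: a later date is not a stated rule, and with nothing in the revision history a deliberate tightening cannot be told from an oversight.

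The second argument is size. The 25% and 57% figures need an IF of 0.80 and an assumed high-dose effect that neither document gives. The SAP footnotes in 7.4.1.1.1 and 7.4.2.1 drop the ESA-dose covariate because too few subjects fell in the high-dose group, which points to the bottom row of the table. This largely stands and is why the practical effect is rated probably small. No IF is reported, though, so the size cannot be fixed.

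Thirdly, the SAP already refers to data review and to input received after soft lock. Reopening the permissive gate now would risk a data-informed choice. That is a fair warning, and it favours settling on the SAP gate.

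**Conclusion.** The concern holds. The documents give opposite confirmatory status to the key secondary endpoints in the same outcome, one that both call a success, and nothing in either resolves it. The contradiction can be read directly from the text and needs no assumption. Its frequency does: 2.8% on the planning assumptions at IF 0.80, and 0.45% to 1.7% at IF 0.97 across the high-dose effects considered. It is large only if the IF is near 0.80 and the high-dose stratum is well beyond the margin. It should be fixed, because the correction is cheap and the ambiguity concerns which claims may be made.

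**What to change.** State one gate, the population tested and the alpha carried forward, in the same words, in the Protocol synopsis and 7.4.2 and in SAP 7.4.1.1.1 and 7.4.2. Add a dated reason to the SAP revision history, and do this before hard lock. The simplest text adopts the SAP gate:

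> Key secondary endpoints are formally tested, in the total population and in the fixed sequence, at one-sided 0.025, only if both H_A0 and H_B0 are rejected. If exactly one is rejected, key secondary results are descriptive.

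This also holds primary-plus-secondary error at 0.025 without further allocation. If the sponsor prefers the protocol's single-null route, both documents must name the population and the alpha for the secondaries in that branch, because the chain already passes the full 0.025 to the other primary null.

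The cost is wording, although the protocol part needs a formal amendment under Protocol 8.3.3. The SAP gate gives up formal secondary claims after a single-null success, including the protocol's subgroup-only route, with the probabilities tabulated above. Keeping the protocol route avoids that loss but requires the explicit alpha statement.
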